9.2.4. Optivate® Exposure Days

An exposure day is defined as a day in which the subject has received at least one dose of Optivate[®]. The number of exposure days will be listed for each subject. Descriptive statistics will be presented for the number of exposure days per subject.

For each subject the number of exposure days per month and the number of exposure days per year will be calculated as follows:

Number of exposure days per year = $\frac{\text{Number of exposure days captured during the study}}{\text{Time on study}} \times 365$

Number of exposure days per month = Number of exposure days captured during the study x 28

Time on study

where time on study = Date of Visit 4 (end of study visit)/withdrawal visit - Date of Baseline visit + 1

These will also be summarised.

Summaries of exposure days will be based on both the Per Protocol Population and Safety Population. NB: In the case of treatment for surgery, if anti-fibrinolytic agents have been administered (pre or post surgery) then these exposure days will be excluded from the Optivate® exposure day calculation.

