7.9.2 FVIII Inhibitors

Both a FVIII inhibitor screen and a quantitative FVIII Nijmegen-Bethesda inhibitor test will be performed at Addenbrooke's Hospital, UK. All inhibitor samples will be collected after a 3 day washout period, when it is anticipated that the pre-substitution FVIII level has reached a nadir¹².

FVIII inhibitor screening test

For the FVIII inhibitor screens, an APTT is performed on a 50/50 mix of a subject's plasma and normal pooled plasma, and compared with the APTT for the subject's plasma and that of normal pooled plasma. A positive inhibitor screen is defined as one that does not correct the APTT by > 50% of the difference between the subject's value and the normal pooled plasma value. To rule out the presence of a time-dependent inhibitor, 50/50 mixes of the subject's plasma and normal plasma are compared following incubation together or separately for 2 hours at 37°C. Time-dependent inhibition is defined as > 4 seconds' prolongation of the incubated mixture relative to the plasmas incubated separately.

FVIII Nijmegen-Bethesda inhibitor test

A Nijmegen-Bethesda assay will also be performed using the same sample as above. A result of ≥ 0.6 BU confirms that the subject has developed inhibitors to FVIII. If this occurs, the test will be repeated on a separate sample; if both tests are confirmed to be ≥ 0.6 BU this will be reported by

the Investigator as an SAE (see Appendix I). The Central Laboratory will notify both the Contract Research Organisation (CRO) and Sponsor immediately if any sample has a value of ≥ 0.6 BU, even if the repeat analysis has not been conducted.

If there is a discrepancy between the FVIII inhibitor screen and Nijmegen-Bethesda assay result, analyses will be repeated on reserve samples and, if necessary, additional samples from the subject, until an unequivocal result, or a reason for the discrepancy, is obtained.

If necessary, repeat FVIII inhibitor quantitative assays will be performed on reserve samples from earlier timepoints, in an attempt to identify the point at which an immune response was initiated. The subject's progress will be monitored closely and if any additional FVIII inhibitor samples are required, these should be taken in triplicate to allow repeat testing and assessment of possible 'transient' inhibitors.

If required, additional methodologies may be used to detect and quantitate inhibitors to FVIII. Any such methodologies will be described in detail in the clinical study report.

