8.1.2.4 Overall Consumption of Optivate[®]

- 1. Number of exposure days for each subject and per month/subject, per year/subject and overall.
- 2. Total dose in IU/kg of Optivate[®] and average dose per infusion for prophylactic use, to treat a bleed, any additional preventative use and overall use; all analysed on a per subject basis.
- 3. Total number of infusions for prophylactic use, to treat a bleed, any additional preventative use and overall use; all analysed on a per subject basis.
- 4. Mean dose in IU/kg of FVIII per subject/month and per subject/year prophylactically, to treat a bleed, any additional preventative use and overall use; all analysed on a per subject basis.
- 5. Mean number of infusions per subject/month and per subject/year for prophylactic use, to treat a bleed, any additional preventative use and overall use; all analysed on a per subject basis.

For calculation purposes, a month will be defined as 28 days and a year will be defined as 365 days. Where a subject has completed less than a year of Optivate[®] treatment, the data will be extrapolated to calculate the per consumption per year.

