9 SUBJECT WITHDRAWAL

Subjects may stop study treatment for any of the following reasons:

• Withdrawal of consent.

- Significant protocol deviation.
- Lost to follow-up.
- Incidental illness.
- Occurrence of adverse events (AEs) not compatible with the continuation of the subject's participation in the study, in the Investigator's opinion (*eg* anaphylactic or other severe/serious reaction to infusion, development of inhibitor).
- Investigator's request.
- Requirement for therapeutic intervention prohibited by the protocol *eg* FVIII containing product or antifibrinolytics agents (expect during surgery).
- Premature termination of the trial by BPL on account of an unacceptable risk-benefit ratio. If this occurs, BPL or BPL's representatives will notify the regulatory authorities, ethics committees and Investigators of the reason for premature study termination, within 15 days from the study being halted.
- Subject/guardian is unco-operative and non-compliant with respect to provisions of the protocol.
- Trial stopped by BPL as 10 evaluable subjects have 100 EDs with Optivate[®].
 NB:this may mean that the last two subjects enrolled into the study may receive a shorter treatment period.

The clinical Investigator may also remove a subject if, in his/her opinion, it is in the best interests of the subject.

Subjects are free to withdraw from the study at any time without providing reason(s) for withdrawal and without prejudice to further treatment. The reason(s) for withdrawal will be documented where possible, particularly where withdrawal is a consequence of an adverse event. The subject's primary care physician (where applicable) will be informed of the reason for withdrawal.

Data collected up until a subject's withdrawal from the study, including data for screen failures, will be retained on the clinical database and used in the analysis and clinical study report.

Subjects withdrawing from the study will be requested to complete the same final assessments as subjects completing the study according to the protocol, particularly safety assessments (see Section 7.4). If there is a medical reason for withdrawal, the subject will remain under the supervision of the Investigator until in satisfactory health or the subject's condition has stabilised.

Reasonable efforts will be made to contact subjects who are lost to follow-up. These efforts must be documented in the subject's medical records.

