9.2.5. Optivate® Consumption

Total dose in IU/kg of Optivate® and average dose per infusion per subject will be summarised overall and by the following categories:

- Prophylactic use
- To treat a bleed
- Additional preventative use
- Other reason

The total number of infusions of Optivate® per subject will be summarized overall and by the above categories.

Total dose and total number of infusions, overall and by the above categories will also be summarized on a per year and on a per month basis. These will be calculated as for the number of exposure days per year/per month, described in Section 9.2.4.

Sponsor: BPL

Protocol: 8VWF07

Version: 1.0

Statistical Analysis Plan

The average dose of Optivate® per infusion across all infusions will also be summarized. Summaries will be based on both the Per Protocol Population and Safety Population.

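### Annualised exposure days, dose and infusions run to the withdrawal visit, so a subject who stops Optivate well before it has an understated rate in the Safety Population (minor)

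*SAP*

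**What the plan says.** SAP 9.2.4 defines the numerator by day of dosing: "An exposure day is defined as a day in which the subject has received at least one dose of Optivate". It multiplies exposure days over time on study by 365 or 28, "where time on study = Date of Visit 4 (end of study visit)/withdrawal visit - Date of Baseline visit + 1". SAP 9.2.5 carries this to total dose and number of infusions, overall and by reason for use: "These will be calculated as for the number of exposure days per year/per month, described in Section 9.2.4". On populations it adds: "Summaries will be based on both the Per Protocol Population and Safety Population". Early withdrawals therefore enter the Safety summaries.

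Protocol 8.1.2.4 speaks of treatment time: "Where a subject has completed less than a year of Optivate[®] treatment, the data will be extrapolated to calculate the per consumption per year". Protocol 10.6.2 repeats the idea for consumption and exposure days. SAP section 12 declares no change from the protocol.

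Protocol section 9 lists reasons to stop study treatment, among them an adverse event, an inhibitor, and "Requirement for therapeutic intervention prohibited by the protocol". It then asks withdrawing subjects to complete the final assessments, with no time limit after the last infusion. Protocol 7.9.2 adds: "All inhibitor samples will be collected after a 3 day washout period".

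**The concern.** A consumption rate describes use while a subject is on the product. Once Optivate has stopped, routine use is zero, but the SAP clock runs until the withdrawal visit. The longer the visit is delayed, the lower that subject's reported exposure days, dose and infusions per year and per month. The effect runs in one direction and falls only on subjects who left Optivate early.

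These rates are named secondary efficacy endpoints in SAP 5.2. With about 12 subjects, each carries about one-twelfth of a Safety Population mean, and two withdrawals are what the enrolment target of 12 for 10 evaluable subjects allows for.

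**Working it through.** The plan states no annualised rate, so there is no figure to reproduce. The check applies the SAP 9.2.4 formula directly.

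**Inputs**
- Month 28 days and year 365 days (Protocol 8.1.2.4, SAP 9.2.4).
- Three prophylactic infusions a week (Protocol 6.2), used for illustration: 3/7 × 365 = 156.4 exposure days a year.
- T = days from the Baseline visit to the last regular Optivate infusion, both days counted. This is an assumption.
- g = days from that infusion to the withdrawal visit. This is also an assumption.
- A regular infusion means any Optivate infusion other than the recovery bolus at the final visit.

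**Formulas**
- SAP denominator: T + g.
- Comparison denominator: T + 3 when g is at least 3. The 3 days match the washout that completers also have before Visit 4, so that interval is not counted as error.
- With the same numerator, understatement = 1 − (T + 3)/(T + g).

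**One subject**

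| T | g | (T + 3)/(T + g) | Understatement |
|---|---|---|---|
| any | 3 | 1 | 0% |
| 28 | 7 | 31/35 | 11% |
| 28 | 14 | 31/42 | 26% |
| 28 | 28 | 31/56 | 45% |
| 60 | 7 | 63/67 | 6% |
| 60 | 14 | 63/74 | 15% |
| 60 | 28 | 63/88 | 28% |

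For T = 28 and g = 14 there are 28 × 3/7 = 12 exposure days. The SAP gives 12/42 × 365 = 104.3 a year. The comparison period gives 12/31 × 365 = 141.3. At a constant dose per infusion, dose and infusion rates shrink by the same factor.

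If the withdrawn subject also receives the final-visit bolus, the SAP numerator gains one day: 13/42 × 365 = 113.0. That is still 20% below 141.3.

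**Group mean, 10 subjects at 156.4 and 2 withdrawn**

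SAP mean = (10 × 156.4 + 2 × 156.4 × T/(T + g))/12. Comparison mean = (10 × 156.4 + 2 × 156.4 × T/(T + 3))/12.

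| T | g | SAP mean | Comparison mean | Change |
|---|---|---|---|---|
| 60 | 14 | 151.5 | 155.2 | −2.4% |
| 28 | 14 | 147.7 | 153.9 | −4.0% |
| 60 | 28 | 148.1 | 155.2 | −4.5% |
| 28 | 28 | 143.4 | 153.9 | −6.8% |

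**Who is affected**
- Completers: no. Visit 4 includes an Optivate bolus (Protocol 4.1), so the period ends on a dosing day.
- Subjects stopped because 10 others reached 100 exposure days: no gap is implied. They are on Optivate until their End-of-Study visit (Protocol 4.2).
- Per Protocol subjects: only someone who stops after 100 exposure days but before the final visit.
- Subjects who stop for an adverse event, an inhibitor or another FVIII product and attend later: yes, in the Safety summaries.

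**The case against.** The case for leaving the SAP alone is fair in most respects. Per Protocol is the primary efficacy population, and the Safety Population is secondary for these endpoints (SAP 6.1, 6.2). Total exposure days, total dose, total infusions and dose per infusion do not use this denominator. The per-subject values are listed, so a reader can see an odd one among about 12 subjects. The permitted prophylactic dose runs from 20 to 40 IU/kg, a twofold range that dwarfs a shift of a few percent in a mean. All of this stands and sets the severity. It does not make the formula right for a subject who has left Optivate.

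Four stronger readings are tempting, and the documents do not support them.
- **The SAP contradicts the protocol.** Protocol 8.1.2.4 ties extrapolation to Optivate treatment but gives no divisor. The SAP supplies one that fits the intent poorly for some withdrawals.
- **Every withdrawal is biased.** The gap needs a subject who stops Optivate and a delayed visit. No delay is stated, and it may be short.
- **The 3-day washout itself is an error.** It precedes every recovery visit, including Visit 4 for completers.
- **Bleed rates are inflated.** SAP 9.2.3 asks for bleeds per year and per month but states no denominator and does not cite 9.2.4. A large inflation appears only if a whole bleed is assumed to fall in the gap. At an assumed 3 bleeds a year, 14 days would hold 3 × 14/365 = 0.12 bleeds. If the bleed rate is the same in the gap, numerator and denominator grow together. Removing bleeds after a stop for an adverse event or inhibitor would depend on outcome and favour the product.

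One further objection concerns the remedy. Protocol 6.2.2.1 allows a twice-weekly regimen by agreement, where intervals can reach 4 days, so a 3-day allowance is a convention. Using 4 days would change a 28-day subject's denominator from 31 to 32 days, about 3%.

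**Conclusion.** The point holds and is minor. As written, SAP 9.2.4 and 9.2.5 understate annualised and monthly exposure days, dose and infusions in the Safety Population for a subject who stops Optivate more than 3 days before the withdrawal visit. For treated periods of 28 or 60 days and gaps of 7 to 28 days, the subject-level understatement is 6% to 45%. With 2 of 12 such subjects and gaps of 14 to 28 days, the mean falls by about 2.4% to 6.8%. These sizes rest on assumed treated periods, gaps and number of withdrawals, and on three infusions a week. The effect is zero if the visit falls within 3 days of the last regular infusion.

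The primary inhibitor endpoint is untouched, and Per Protocol rates almost certainly are too. A reader might infer that bleed results are biased as well. The documents leave the bleed denominator unstated, which does not establish a bias.

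**What to change.** In SAP 9.2.4, and through it 9.2.5, keep Visit 4 as the end date for completers. For withdrawn subjects, end the rate period for exposure days, dose and infusions at the earlier of the withdrawal visit and the last regular Optivate infusion plus 3 days. Count all three quantities within that same period. Keep time on study as defined in SAP 8.1 for disposition and study duration.

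Leave all bleeds in the SAP 9.2.3 tables. At most, flag in the bleed listing those that start after Optivate was stopped.

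The cost is one sentence and one derived date. Infusion dates are already in the study diary (Protocol 7.8), and the most recent dose before each visit is already listed (SAP Listing 14). Rates for withdrawn subjects would no longer share a denominator with the study-duration table, so a footnote should say so.

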9.2.5. Optivate® Consumption

Total dose in IU/kg of Optivate® and average dose per infusion per subject will be summarised overall and by the following categories:

- Prophylactic use
- To treat a bleed
- Additional preventative use
- Other reason

The total number of infusions of Optivate® per subject will be summarized overall and by the above categories.

Total dose and total number of infusions, overall and by the above categories will also be summarized on a per year and on a per month basis. These will be calculated as for the number of exposure days per year/per month, described in Section 9.2.4.

Sponsor: BPL

Protocol: 8VWF07

Version: 1.0

Statistical Analysis Plan

The average dose of Optivate® per infusion across all infusions will also be summarized. Summaries will be based on both the Per Protocol Population and Safety Population.

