8.1.2.2 Optivate[®] Recovery Over Time

For V1 (1 ED), V2 (10-15 ED), V3 (50-75 ED) and V4 (100 ED) recovery will be calculated using the formula in 8.1.2.1. An overall Optivate[®] recovery value will be calculated across the whole study and for each batch on a per subject basis. An ANOVA will also be performed to compare recovery values at V1, V2, V3, and V4 and across batches.

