10.6.2 Secondary Endpoints

The secondary efficacy endpoints are the parameters described in Section 8.1.2 and safety variables in Section 8.2.

Recoveries

Results will be tested for the normality of distribution using the Shapiro-Wilk test and if normality is confirmed, an ANOVA will be performed for the recovery comparison (See Section 8.1.2.1 and 8.1.2.2).

Descriptive statistics will be presented on the number of recoveries at each timepoint and for each subject. These will be presented for each visit and for each subject and then for each batch of FVIII/ Optivate[®] used (see Section 8.1.2.1 and 8.1.2.2). Overall descriptive statistics will also be present for all subjects and all batches.

Bleeds

Bleed data will be summarised using summary statistics on two different bases: with each bleed as the experimental unit, and also with each subject as the experimental unit. Severity, duration of bleed, location and cause of bleed will be summarised separately, as well as being summarised in total. The treatment of new bleeds and ongoing bleeds will be listed. Also see Section 8.1.2.3.

Clinician's and subject's judgement of break-through bleed of treatment outcome

The data for clinician's and subject's assessment of bleeds will tabulated on separate tables, including the count for the number of bleeds not assessed. The tables will display the number and percentage of bleeds assessed for each category (*eg* very helpful, helpful etc.). This will be presented: Using all bleeds as the denominator and also the number of bleeds assessed as the denominator, displaying the number of bleeds not assessed.

Optivate[®] consumption

Dosing data will be summarised by treatment type *ie* prophylactic, preventative, to treat a bleed and overall. Total consumption data will be summarised using summary statistics on a per infusion and a per subject basis. Overall consumption data will be listed for each subject and summary statistics will also be displayed per month and year on a per subject basis (also see Section 8.1.2.4). Where a subject has completed less than a year of Optivate[®] treatment, the data will be extrapolated to calculate the per year consumption.

Exposure days

An exposure day is defined as a day in which the subject has received at least one dose of Optivate[®] (irrespective of treatment). The number of EDs will be listed for each subject. Descriptive statistics will be presented on a per month, per year and overall basis (also see Section 8.1.2.4).

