7. GENERAL ASPECTS FOR STATISTICAL ANALYSIS

7.1. GENERAL METHODS

Statistical outputs will be generated using SAS version 9.3 (or later).

The study only has one treatment and so all summary tables will have a single results column for Optivate[®]. However, if subjects suffering from severe haemophilia A with basal FVIII values of < 2% rather than < 1% are recruited into the study, an additional two results columns will be presented, one for subjects with a basal FVIII < 1%, and one for subjects with a basal FVIII $\ge 1\%$ (see Section 6.3).

Continuous variables will be summarised using the number of observations (n), mean, 95% confidence interval for the mean, standard deviation (SD), median, minimum, and maximum. Minima and maxima will be quoted to the number of decimal places as recorded in the CRF, means and medians will be quoted to one further decimal place, and SDs will be quoted to one further decimal place than the mean value. Categorical variables will be summarised using number of observations (n), frequency and percentages of subjects. Percentages will be rounded to one decimal place, with the exception of 0% and 100%, which will be presented to no decimal places.

All relevant subject data will be included in listings. All subjects entered into the database will be included in subject data listings.

Data from unscheduled visits will not be included in the summary tables. These data will be listed only.

Where multiple data/results are available at a given visit for the same parameter, the first non-missing result will be used in the summary tables. All data will however be listed.

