9.2. SECONDARY EFFICACY ENDPOINTS AND ANALYSES

9.2.1. Recovery with current FVIII (Screening Visit) versus 1st dose with Optivate® (Visit 1)

All recoveries will be calculated from incremental FVIII values (i.e. actual values minus pre-infusion values) using the vial label content as provided by BPL. FVIII values of less than 0.01 IU/mL will be regarded as zero. Incremental recovery will be determined from the peak value reached within 70 minutes post-infusion, samples taken after this time point will be discussed with the Sponsor and a decision whether to exclude the result will be made. Calculations will be based on the peak values obtained at actual post-infusion times, rather than those scheduled in the protocol.

Sponsor: BPL

Protocol: 8VWF07

Version: 1.0

Statistical Analysis Plan

FVIII levels will be reported in IU/dL and will be converted to IU/dL for the listings and calculation of incremental recovery.

Recovery = $\frac{\text{FVIII increment (IU/dL)}}{\text{FVIII dose (IU/kg)}}$

Recovery with current FVIII and first dose with Optivate® will be summarised.

Results will be tested for the normality of distribution using the Shapiro-Wilk test and if there is no strong evidence against normality, an Analysis of Variance (ANOVA) will be performed for the above recovery comparison.

The ANOVA model will include factors for subject and FVIII product (current FVIII versus Optivate®). Adjusted means for each product will be presented, in addition to the estimate and 95% confidence interval for the difference between products. The p-value for the hypothesis of equal recovery between the products will also be presented.

The analysis will be performed on both the Per Protocol and the Safety populations.

9.2.2. Recovery at 1 ED (Visit 1), 10-15 EDs (Visit 2), 50-75 EDs (Visit 3) and 100 EDs (Visit 4)

For Visit 1 (1 ED), Visit 2 (10-15 ED), Visit 3 (50-75 ED) and Visit 4 (100 ED), recovery will be calculated using the formula in 9.2.1.

Recovery will be summarised by visit, batch and subject.

An ANOVA will be performed to compare recovery values at Visit 1, Visit 2, Visit 3 and Visit 4. The model will include factors for subject and visit. Adjusted means for each visit will be presented, in addition to the estimates and 95% confidence intervals for the differences between visits. The p-value for the hypothesis of equal recovery between visits will also be presented.

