An ANOVA will be performed to compare recovery values for each batch. The model will include factors for subject, visit and batch. Adjusted means for each batch will be presented, in addition to the estimates and 95% confidence intervals for the differences between batches. The p-value for the hypothesis of equal recovery between batches will also be presented.

The primary analysis will be performed using the Per Protocol Population. A secondary analysis will be conducted on the Safety Population. The summary by subject will be for the Safety population only.

Sponsor: BPL

Protocol: 8VWF07

Version: 1.0

Statistical Analysis Plan

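### SAP 7.1's default 95% CI for the mean treats repeated records as independent; on the all-infusions dose summary it would be about 3 to 11 times too narrow

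*SAP*

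**What the plan says.** The default is in SAP 7.1: "Continuous variables will be summarised using the number of observations (n), mean, 95% confidence interval for the mean, standard deviation (SD), median, minimum, and maximum". No later section exempts summaries in which a subject appears more than once.

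Three summaries have a unit smaller than the subject:

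- **Dose (SAP 9.2.5).** The subject-level summary comes first: "Total dose in IU/kg of Optivate® and average dose per infusion per subject will be summarised overall". A pooled one is then added: "The average dose of Optivate® per infusion across all infusions will also be summarized". This follows Protocol 10.6.2: "Total consumption data will be summarised using summary statistics on a per infusion and a per subject basis".
- **Bleed duration (SAP 9.2.3).** A note makes the bleed, not the subject, the unit of the summary.
- **Recovery (SAP 9.2.2).** "Recovery will be summarised by visit, batch and subject". The by-batch summary pools visits. Protocol 8.1.2.2 asks for an overall recovery value across the study and "for each batch on a per subject basis". The formal batch comparison is an ANOVA: "The model will include factors for subject, visit and batch".

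Protocol 10.3 also includes a 95% CI for the mean in its default summary, but defines n as subjects, not observations.

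**The concern.** A one-sample t interval is valid when the records are independent. Infusions within a subject are not: the routine dose is agreed for each subject within 20-40 IU/kg (Protocol 6.2.2.1), and the preventative dose is fixed for each individual (Protocol 6.2.2.3). An interval over 1,000 or more infusions therefore describes a study of that many unrelated doses, when the information on the mean comes from about 10 people.

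The report would then carry two intervals for closely related quantities, one over subjects and one over infusions. The second would be several times narrower, with nothing to mark it as unreliable. The same applies to bleed duration when some subjects bleed repeatedly, and to recovery by batch when a subject's visits fall in the same batch.

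**Working it through.** The plan states no interval width, SD or within-subject correlation, so there is no figure of its own to reproduce.

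**Inputs**

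- Subjects: k = 10 evaluable (SAP 4.3).
- Infusions per subject: at least 100, since the per-protocol set needs 100 exposure days (SAP 6.1). Three a week gives 3 × 39 = 117 to 3 × 52 = 156 over the expected 39 to 52 weeks. I use m = 100.
- Recoveries per subject: up to m = 4 (Visits 1 to 4). SAP 4.5 aims to keep each subject on one batch as far as supply allows.
- Intraclass correlation ρ: not in the documents, so assumed and shown as a range.

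**Formulas**

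Design effect: DEFF = 1 + (m − 1)ρ.
Width ratio (subject-level CI to pooled CI) = √DEFF × t(0.975; k − 1) / t(0.975; km − 1).

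Coverage of the pooled CI was simulated with a normal random subject effect, 20,000 runs per setting.

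**Dose over all infusions** (k = 10, m = 100, 1,000 records). The t quotient is 2.262/1.962 = 1.153. At ρ = 0.05, DEFF = 1 + 99 × 0.05 = 5.95, √5.95 = 2.44, and 2.44 × 1.153 = 2.8.

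| ρ (assumed) | DEFF | Effective records | Width ratio | Coverage of nominal 95% CI |
|---|---|---|---|---|
| 0.05 | 5.95 | 168 | 2.8 | 58% |
| 0.1 | 10.9 | 92 | 3.8 | 44% |
| 0.3 | 30.7 | 33 | 6.4 | 27% |
| 0.5 | 50.5 | 20 | 8.2 | 21% |
| 0.9 | 90.1 | 11 | 10.9 | 15% |

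The interval over 10 subject means kept 95% coverage throughout.

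In dose units, assume subject doses uniform on 20-40 IU/kg (SD 20/√12 = 5.77):

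- Within-subject SD 2: pooled half-width 1.962 × √(5.77² + 2²)/√1000 = 0.38 IU/kg; subject-level half-width 2.262 × √(5.77² + 2²/100)/√10 = 4.13 IU/kg. Ratio 10.9.
- Within-subject SD 6: 0.52 against 4.15 IU/kg. Ratio 8.0.

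**Recovery by batch** (m = 4, all four recoveries in one batch). Here √DEFF cannot exceed 2. The t quotient is 2.262/2.023 = 1.12 with 10 subjects in the batch and 4.303/2.201 = 1.95 with three.

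| ρ (assumed) | Width ratio, 10 subjects | Coverage | Width ratio, 3 subjects | Coverage |
|---|---|---|---|---|
| 0.3 | 1.5 | 84% | 2.7 | 84% |
| 0.5 | 1.8 | 78% | 3.1 | 76% |
| 0.7 | 2.0 | 72% | 3.4 | 69% |

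With three subjects, a large part of the ratio is the t quantile on 2 degrees of freedom. At ρ = 0, or with one recovery per subject per batch, the pooled interval has its nominal coverage.

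**Bleed duration.** The same formulas apply, but the documents give no number of bleeds per subject, so I put no size on it.

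**The case against.** Several points on the other side stand.

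- **The CI in these tables is inferred.** Neither SAP 9.2.5 nor 9.2.2 mentions a CI for these descriptive summaries; it comes from the SAP 7.1 default. The mock-ups are a separate attachment that I have not seen, and the sample layout in SAP 14.2.5.2 shows no CI. This limits the point to what the default rule produces as written.
- **The meaning of n is not uniform.** A reader might infer that protocol and SAP share a record-level n. They do not: Protocol 10.3 and SAP 14.2.4 describe n as subjects. Only SAP 7.1 says observations.
- **The endpoint is not the pooled summary.** A reader might infer that the secondary endpoint itself would be reported with false precision. SAP 5.2 defines average dose per infusion on a per-subject basis, and SAP 9.2.5 summarises it that way. The pooled figure is supplementary.
- **Batches are compared by a model.** A reader might infer that the batch comparison rests on the raw intervals. The planned ANOVA has a subject factor. How well it can separate batch from subject when subjects stay on one batch is a different question.
- **Protocol 8.1.2.2 is loosely worded.** Protocol 10.6.2 separately asks for descriptive statistics by visit, subject and batch, which SAP 9.2.2 follows. I do not treat the by-batch summary as a clear departure from the protocol.

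That the summaries are descriptive is a weaker defence, since a CI is a statement about precision. None of these points makes an infusion-level interval valid where the default rule produces one.

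**Conclusion.** The point holds for the pooled dose summary: applied as written, SAP 7.1 gives an interval about 3 times too narrow at ρ = 0.05 and 8 to 11 times at 0.5 to 0.9. The correlation is assumed, but doses set subject by subject make the upper part of that range plausible, and even 0.05 leaves coverage at 58%.

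Bleed duration has the same fault, of unknown size. For recovery by batch the interval is about 1.5 to 2 times too narrow with 10 subjects in a batch and about 3 times with three, provided that a subject's four recoveries share a batch and ρ is 0.3 to 0.7 (assumed). Calling the batch intervals far too narrow in general would go beyond what the documents support.

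No inhibitor result, planned test or defined dose endpoint changes. This is a correction to make before the tables are produced, not a threat to the study's main conclusion.

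**What to change.** 1. **SAP 7.1:** state that 95% CIs for means are given only where each subject contributes one value, and align the definition of n with Protocol 10.3 and SAP 14.2.4.
2. **SAP 9.2.5 and 9.2.3:** for dose across all infusions and duration across all bleeds, keep the mean, SD, median and range and drop the CI. Quote the dose CI from the per-subject averages already planned (degrees of freedom = subjects − 1).
3. **SAP 9.2.2:** for recovery by batch, average each subject's recoveries within the batch and compute the CI over those subject means, or omit it.
4. **All three:** show the number of subjects and the number of records.

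The cost is SAP wording and changes to the affected table shells, with no new data or patients. Reported intervals become wider, and a batch used by only one subject has no CI.
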